### 3.1.4 Follow-up

The follow-up assessments will be performed 30 days ( $\pm 2$  days) after the [ $^{14}\text{C}$ ]BTZ-043 dose.

Assessments during follow-up will be performed as presented in the schedule of assessments (Table 1).

## 3.2 Discussion of Study Design

The current design is commonly used for AME studies and in accordance with the current EMA “Guideline on the investigation of drug interactions”. Since the present study is a descriptive study aimed at assessing excretion routes of BTZ-043 and evaluating mass balance, a formal statistical sample size calculation was not performed. A sample size of 4 subjects is a minimum, accepted number of subjects for AME studies and is considered sufficient to achieve the study objectives. Early-termination subjects may be replaced if the total number of completers drops below 4, after mutual agreement between the Sponsor and PRA.

### 3.2.1 COVID-19 Risk Mitigation

This study will be conducted in accordance with guidance from the Central Committee on Research Involving Human Subjects (CCMO [Centrale Commissie Mensgebonden Onderzoek], ie, the Dutch competent authority [CA]) on conducting Phase 1 trials in clinical research centers in The Netherlands during the COVID-19 pandemic.

During the entire study, the clinical research center will implement all recommendations issued by the Dutch government, including specific guidelines related to clinical research executed in clinical research centers with respect to minimizing the risk of disease spreading (eg, social distancing, disinfection, hygiene, and wearing of personal protection equipment by study staff). Details on specific procedures are described in the site specific manual.

In cases where subjects are not able to attend study visits due to an infection with SARS-CoV-2, the Investigator will discuss with the Sponsor potential mitigation approaches (including, but not limited to, extending the visit window, conducting evaluations via video link or phone call, allowing for safety procedures to be conducted at a local facility). The rationale (eg, the specific limitation imposed by the SARS-CoV-2 infection that led to the inability to perform the protocol-specified assessment) and outcome of the discussion will be documented in the electronic case report form (eCRF).

In addition, the following containment measures will be taken during the study:

- Polymerase chain reaction (PCR) testing for SARS-CoV-2 will be performed at the time points indicated in [Table 1](#).
- A subject should not be admitted if there was any contact with a person who tested positive for SARS-CoV-2 or a COVID-19 patient within the last 2 weeks prior to admission to the clinical research center.
- If a subject is tested to be SARS-CoV-2 positive on Day -1, the subject will be excluded from participation with reference to Exclusion Criterion 13, and referred for treatment.
- Physical examinations will be limited.
- If a subject becomes ill and/or is tested to be SARS-CoV-2 positive after the administration of study treatment, study assessments will be stopped (see also [Section 3.3.3.1](#)). A safety follow-up can be done if deemed necessary by the Investigator. The subject will be kept in-house in quarantine with appropriate medical intervention until complete elimination of the study compound or will be asked to quarantine at home according to guidelines of the Dutch government.

### 3.3 Selection of Study Population

#### 3.3.1 Inclusion Criteria

Note: Restrictions that apply to the period after admission are described in [Section 3.4.9](#), except when they concern a statement of willingness.

The following inclusion criteria must be met for a subject to be eligible for inclusion in the study:

1. Sex : male
2. Age : 18 years to 55 years, inclusive, at screening.
3. Body mass index (BMI) : 18.0 to 29.0 kg/m^2, inclusive, at screening.
4. Weight : 55 to 90 kg, inclusive, at screening.
5. Status : healthy subjects.
6. Male subjects, if not surgically sterilized, must agree to use adequate contraception and not donate sperm from admission to the clinical research center until 90 days after the follow-up visit. Adequate contraception for the male subject (and his female partner, if she is of childbearing potential) is defined as using hormonal contraceptives or an intrauterine device combined with at least 1 of the following forms of contraception: a diaphragm, a cervical cap, or a condom. Total abstinence, in accordance with the lifestyle of the subject, is also acceptable.
7. All prescribed medication must have been stopped at least 30 days prior to admission to the clinical research center.
8. All over-the-counter medications, vitamin preparations (especially vitamin C), other food supplements, and herbal medications (eg, St. John's wort) must have been stopped at least 14 days prior to admission to the clinical research center. An exception is made for paracetamol, which is allowed up to 48 hours prior to study drug administration.
9. No vaccination within 14 days prior to study drug administration.

10. Ability and willingness to abstain from alcohol from 48 hours (2 days) prior to screening and admission to the clinical research center.
11. Ability and willingness to abstain from methylxanthine-containing beverages or food (coffee, tea, cola, chocolate, and energy drinks), grapefruit (juice), corn (whole corn kernels and popcorn), cruciferous vegetables, and bitter oranges from 48 hours (2 days) prior to admission to the clinical research center.
12. Good physical and mental health on the basis of medical history, physical examination, clinical laboratory, ECG, and vital signs, as judged by the Investigator.
13. Willing and able to sign the ICF.

### 3.3.2 Exclusion Criteria

Note: Restrictions that apply to the period after admission are described in Section [3.4.9](#), except when they concern a statement of willingness.

A subject who meets any of the following exclusion criteria will not be eligible for inclusion in the study:

1. Participation in another study with a radiation burden of  $>0.1$  mSv and  $\leq 1$  mSv in the period of 1 year prior to screening; a radiation burden of  $>1.1$  mSv and  $\leq 2$  mSv in the period of 2 years prior to screening; a radiation burden of  $>2.1$  mSv and  $\leq 3$  mSv in the period of 3 years prior to screening, etc.
2. Exposure to radiation for diagnostic reasons (except dental X-rays and plain X-rays of thorax and bony skeleton [excluding spinal column]), or during work within 1 year prior to drug administration.
3. Irregular defecation pattern (less than once per day on average).
4. Employee of PRA, Nuvisan, or the Sponsor.
5. History of relevant drug and/or food allergies.
6. Using tobacco products within 60 days prior to drug administration.
7. History of alcohol abuse or drug addiction (including soft drugs like cannabis products).
8. Positive drug and alcohol screen ( opiates, methadone, cocaine, amphetamines [including ecstasy], cannabinoids, barbiturates, benzodiazepines, gamma-hydroxybutyric acid, tricyclic antidepressants, and alcohol) at screening or admission to the clinical research center.
9. Average intake of more than 24 grams of alcohol per day.
10. Positive screen for hepatitis B surface antigen (HBsAg), hepatitis C virus (HCV) antibodies, or HIV 1 and 2 antibodies.
11. Participation in a drug study within 30 days prior to drug administration in the current study. Participation in more than 4 drug studies in the 12 months prior to drug administration in the current study.
12. Donation or loss of more than 450 mL of blood within 60 days prior to drug administration. Donation or loss of more than 1.5 liters of blood in the 10 months prior to drug administration in the current study.
13. Significant and/or acute illness within 5 days prior to drug administration that may impact safety assessments, in the opinion of the Investigator.

14. Unwillingness to consume the Food and Drug Administration (FDA)-recommended high-fat breakfast.
15. Unsuitable veins for infusion or blood sampling.
16. Positive nasopharyngeal PCR test for SARS-CoV-2 on Day -1.

Please note that subjects should refrain from consumption of any foods containing poppy seeds, corn (whole corn kernels and popcorn), cruciferous vegetables, and bitter oranges within 48 hours (2 days) prior to screening and admission to the clinical research center to avoid false positive drug screen results, difficult feces texture, or induction of drug metabolizing enzymes. In addition, they should refrain from strenuous exercise within 96 hours (4 days) prior to screening and admission as this could result in abnormal clinical laboratory values.

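### Exclusion criterion 1 leaves gaps between its radiation tiers, so a prior-study burden of 1.1 mSv six months before screening passes while 0.2 mSv is excluded

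*Protocol*

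**What the plan says.** Protocol Section 3.3.2, criterion 1, concerns "Participation in another study with a radiation burden of" a stated size, with a look-back that lengthens as the burden rises:

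- above 0.1 and up to 1 mSv: 1 year before screening;
- above 1.1 and up to 2 mSv: 2 years before screening;
- above 2.1 and up to 3 mSv: 3 years before screening, after which the series is left to continue.

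The first tier ends and the second begins at the words "in the period of 1 year prior to screening; a radiation burden of", and the list closes with "mSv in the period of 3 years prior to screening, etc". The lower bounds are strict and the upper bounds inclusive. The bounds are the same in both copies of the protocol in the released file, and the Summary of Changes does not list Section 3.3.2.

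Two other criteria in the same section bear on the point. Criterion 2 excludes "Exposure to radiation for diagnostic reasons (except dental X-rays and plain X-rays of thorax and bony skeleton" (excluding the spinal column), as well as exposure at work, within 1 year before dosing. Criterion 11 excludes "Participation in a drug study within 30 days prior to drug administration in the current study" and, separately, "Participation in more than 4 drug studies in the 12 months prior to drug administration in the current study".

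**The concern.** Each upper bound (1 and 2 mSv) sits 0.1 mSv below the next strict lower bound (1.1 and 2.1 mSv), so the values in between belong to no tier. The rule is meant to impose a longer look-back on a higher burden. In these two bands it imposes none, although lower burdens on the same date are excluded.

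The people protected by this rule are healthy volunteers for whom Section 1.2 expects no clinical benefit. Screening staff apply exclusion criteria as worded and should not have to infer missing values. The SAP (Section 12.3) will list non-compliance with the eligibility criteria, but a subject in a gap breaches nothing in criterion 1, so that listing would not reveal the case.

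**Working it through.** **Inputs.** All come from protocol Section 3.3.2, criterion 1. Write b for the prior-study burden in mSv and y for the years between that study and screening. Criterion 1 excludes a volunteer if any of these holds:

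- tier 1: 0.1 < b ≤ 1 and y ≤ 1;
- tier 2: 1.1 < b ≤ 2 and y ≤ 2;
- tier 3: 2.1 < b ≤ 3 and y ≤ 3.

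The plan states no figure to reproduce here, so the check is whether the three tiers cover every burden from above 0.1 to 3 mSv.

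**Coverage.** The union of the tiers is (0.1, 1] ∪ (1.1, 2] ∪ (2.1, 3]. Taken out of (0.1, 3], it leaves (1, 1.1] and (2, 2.1]. Each gap is 0.1 mSv wide (1.1 − 1 and 2.1 − 2).

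**Literal result at y = 0.5.**

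| Burden (mSv) | Tier met | Criterion 1 |
|---|---|---|
| 0.2 | 1 | excluded |
| 1.0 | 1 | excluded |
| 1.05 | none | passes |
| 1.1 | none | passes |
| 1.11 | 2 | excluded |
| 2.0 | 2 | excluded |
| 2.05 | none | passes |
| 2.1 | none | passes |
| 2.11 | 3 | excluded |

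**Does rounding remove the gaps?** No. If burdens are recorded to one decimal, there are 30 values from 0.1 to 3.0 mSv. Three meet no tier: 0.1, 1.1 and 2.1. The first is the criterion's own lower limit and is allowed by design, so the real gaps on this grid are the other two. They remain because the lower bounds are strict. The open-ended continuation after the third tier closes neither gap; if it follows the same pattern, it adds further ones.

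**Does another criterion close them?**

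- Criterion 2 is written for diagnostic and work exposure. It does not reach a radiolabel study.
- Criterion 11 reaches drug studies within 30 days before dosing, or more than 4 of them in 12 months. One drug study six months before screening is outside both limits.
- Section 3.3.3 lets the Investigator end a subject's participation for safety. That is discretionary and sets no eligibility threshold.

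**Two ways to close the gaps.**

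| Option | Tiers (mSv) | Look-back for 1.1 mSv | Look-back for 2.1 mSv |
|---|---|---|---|
| A: lower the lower bounds | (0.1, 1], (1, 2], (2, 3] | 2 years | 3 years |
| B: raise the upper bounds | (0.1, 1.1], (1.1, 2.1], (2.1, 3.1] | 1 year | 2 years |

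Under both, 1.1 and 2.1 mSv at six months are excluded, 0.2 mSv stays excluded and 0.1 mSv stays allowed. They differ further back: at y = 1.5, 1.1 mSv is excluded under A (1.5 ≤ 2) and passes under B (1.5 > 1).

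**The case against.** The best counter-argument is that the case is remote. Section 3.4.4 describes 0.1 to 1.0 mSv as acceptable for investigations in small volunteer groups and puts this study's own burden at about 0.16 mSv. A single earlier study within that range falls in tier 1, which has no gap. To land in a gap, a volunteer would need a study above the range, or a total over several studies that happens to fall in a 0.1 mSv band. The criterion does not say whether it means burden per study or in total; the gap is easier to reach on the cumulative reading. This stands, and it limits the reach of the problem without removing it.

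Second, criterion 2 has no dose threshold and no exemption for exposure received inside a study. If the earlier burden came from diagnostic imaging in a trial within the past year, criterion 2 would arguably exclude the volunteer. That also stands, but radiolabel studies and non-diagnostic imaging remain uncovered.

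Third, the intent is plain, and a screening physician who sees 1.0 and 1.2 mSv both excluded is unlikely to admit 1.1 mSv. This lowers the real risk but relies on staff overriding the text.

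Finally, the authors may have meant 1 mSv per year plus a 0.1 mSv allowance, which would put the upper bounds at 1.1 and 2.1. The documents do not say so. The possibility affects the choice of correction, not the need for one.

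**Conclusion.** The concern holds. As written, criterion 1 assigns no look-back to prior-study burdens above 1 and up to 1.1 mSv, or above 2 and up to 2.1 mSv, while excluding lower burdens at the same date. The conclusion rests on the literal bounds and, for the six-month example, on a prior exposure that criteria 2 and 11 do not catch, such as one radiolabel study.

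The documents give no distribution of prior burdens, so the chance that a volunteer is affected cannot be calculated. With 4 subjects to be dosed and at most 2 replacements, it should be very small. Nothing in the PK, mass-balance or safety analysis depends on it. This is a minor correction, worth making because the error is certain and the rule protects participants.

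**What to change.** Reword criterion 1 with contiguous tiers: above 0.1 and up to 1 mSv within 1 year, above 1 and up to 2 mSv within 2 years, above 2 and up to 3 mSv within 3 years, continuing in the same steps. This is option A. It is the safer default because it gives the gap values the longer look-back. Option B is acceptable if a 0.1 mSv allowance was intended. The sponsor's radiation expert should confirm the boundaries, and the same edit could state whether the burden is counted per study or in total.

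The cost is a one-line wording change and, at most, a very rare extra screen failure.

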### 3.3.3 Removal of Subjects from Assessment

Participation in the study is strictly voluntary. A subject has the right to withdraw from the study at any time for any reason.

The Investigator has the right to terminate participation of a subject for any of the following reasons: difficulties in obtaining blood samples, violation of the protocol, severe AEs or SAEs, or for any other reason relating to the subject's safety or integrity of the study data.

If a subject is withdrawn from the study, Nuvisan and LMU Klinikum will be informed immediately. If there is a medical reason for withdrawal, the subject will remain under the supervision of the Investigator until satisfactory health has returned, or the condition has stabilized with no more change being likely.

After signing informed consent, subjects who drop out or withdraw for any reason without completing all screening evaluations successfully as well as subjects who drop out or withdraw prior to the first dose of study drug will be considered screening failures.

A subject who is withdrawn or voluntarily withdraws from the study for any reason, whether related to the study drug or not, after having received the study drug, will be considered an early-termination subject. If a subject is withdrawn from the study, the early-termination subject will be replaced after mutual agreement between the Sponsor and PRA if the number of evaluable subjects drops below 4 (with a maximum of 2 replacements).

The decision regarding the replacement of subjects will be documented.

PRA will make every effort to ensure that early-termination subjects who have received the study drug complete the early-termination assessments/safety follow-up assessments.

Early-termination subjects may be replaced if the total number of completers drops below 4, after mutual agreement between Nuvisan, LMU Klinikum, and PRA.

### 3.3.3.1 Stopping Rules for Individual Subjects

In case of a positive SARS-CoV-2 virus PCR test or evidence for COVID-19 during the study, the subject will be withdrawn from the study. The subject will be isolated from other study participants and referred for treatment. The subject will be followed up in quarantine in the clinical research center until complete elimination of the study compound or will be asked to quarantine at home according to guidelines of the Dutch government.

## 3.4 Treatments

### 3.4.1 Treatments Administered

Subjects will receive a single oral dose of 500 mg BTZ-043 containing 3.7 MBq of [C]BTZ-043 on Day 1.

### 3.4.2 Identity of Investigational Product

#### Active Medication

Active substance	: BTZ-043
Activity	: Inhibition of M. tuberculosis DprE1
In development for	: Tuberculosis
Dose	: 1 x 100 mL (equivalent to 500 mg BTZ-043)
Strength	: 5 mg/mL BTZ-043 containing 0.037 MBq of [  C]BTZ-043
Dosage form	: Oral suspension
Manufacturer	: Sourced by pharmacy at PRA

The active pharmaceutical ingredient will be provided by the Promotor.

[C]BTZ-043 is a drug under development and not approved yet. It will be manufactured and analysed according to Good Manufacturing Practice (GMP) requirements. A GMP certificate of the manufacturer of the [C]BTZ-043 suspension and an Investigator's Brochure that summarizes preclinical and clinical data with respect to BTZ-043 are in place. A certificate of analysis and a certificate of conformity will be provided by PRA prior to clinical part.

For details concerning drug storage and drug accountability see Appendix [8.1](#).

### 3.4.3 Method of Assigning Subjects to Treatment Groups

After obtaining informed consent, subjects will receive a screening number and will be screened according to the inclusion and exclusion criteria. Subjects who have met all eligibility criteria will receive a subject number upon inclusion in the study (Subject Numbers 001-004). They will receive the subject number just prior to dosing. The subject number will ensure identification throughout the study after study drug administration. Replacement subjects will receive the number of the subject to be

replaced, increased by 100 (eg, 101 replacement number for Subject Number 001), and will be administered the same treatment.

After signing informed consent, subjects who drop out or withdraw for any reason without completing all screening evaluations successfully as well as subjects who drop out or withdraw prior to the first dose of study drug will be considered screening failures. Such subjects, and also subjects who are eligible for inclusion in the study but do not receive the study drug, will not receive a subject number, and only applicable data will be entered in the eCRFs.

#### 3.4.4 Selection of Doses and Meals in the Study

The targeted dose of 500 mg is considered a clinically relevant dose for the human AME study (Table 2) since this exposure achieves a maximal bactericidal effect and has shown to be tolerable in the 14-day Phase 1b study. It is proposed that the active pharmaceutical ingredient is taken after a high-fat breakfast (see Section 3.4.7), as absorption is then much improved. As shown in Table 2, the expected exposure is well below the maximum and well tolerated exposure achieved in the Phase 1b study. In the unexpected case that the currently conducted Phase 2a study with 250 mg, 500 mg, and 1000 mg BTZ-043 administered after a high-fat breakfast shows any dose-related safety alert, the study team and the Sponsor will take measures to reduce the exposure. Reduction of exposure will be achieved by adapting the food intake (up to fasting) before the administration of [C]BTZ-043. This protocol describes the drug administration of 500 mg [C]BTZ-043 after a high-fat breakfast as default. However, the study team and the Sponsor will decide whether a reduction in food intake is necessary to reduce the exposure to [C]BTZ-043.

In case it is indeed decided to administer 500 mg [C]BTZ-043 after a standardized breakfast or in the fasted state rather than after a high-fat breakfast as planned, this decision and the associated rationale will be laid down in a Note to File, to be signed by the Sponsor and the PI, and to be submitted to the IEC for information only.

The dose of C (approximately 3.7 MBq) to be administered was chosen to ensure successful profiling and identification of metabolites.

In the present study, the estimated effective radiation burden after a single oral radioactivity dose of 3.7 MBq is approximately 0.16 mSv. For biomedical investigations in small groups of human volunteers, an effective dose of 0.1 to 1.0 mSv is considered acceptable.

#### 3.4.5 Radiation Safety of Clinical and Laboratory Staff

It is expected that the clinical and laboratory staff handling the radioactive material and samples will not be exposed to any relevant radiation and associated health risk. The [C] isotope emits low energy beta particles, which are not able to penetrate the dose containers or sample container walls. Therefore, there will be no “external” exposure from sample handling. The samples from the participants after

radiolabeled dose administration will contain low levels of radioactivity. The radioactive dose of 3.7 MBq [C] per subject is below the legal handling limit, above which a special laboratory and special procedures for handling radioactivity would be required. Therefore, the staff can handle the study samples like any other non-radioactive biological material. Common practice of safe laboratory technique and hygiene will be exercised in handling all biological materials from this study.

### 3.4.6 Timing of Doses in the Study

On Day 1, the study drug will be administered with the subject in the upright position. The study drug will be administered to subjects between 08:00 and 11:00 in the morning. After an overnight fast of at least 10 hours, subjects will receive an FDA-recommended high-fat breakfast (or a standardized breakfast, if applicable as outlined in Section 3.4.4) that will have to be finished within 20 minutes. The entire breakfast must be consumed by the subjects. The actual consumed food will be documented.

Dosing will occur at 30 minutes after the start of the high-fat breakfast (or the standardized breakfast, if applicable, or dosing will occur in a fasted state, if applicable as outlined in Section 3.4.4).

The study drug will be given as an oral suspension of 100 mL, which will be provided in an amber glass bottle from which the subjects can drink. Thereafter the bottle will be rinsed twice with 70 mL of water, and the subjects will be required to drink the bottle contents after rinsing. Thereafter, the subjects are required to drink additional non-carbonated water until they have ingested a total volume of 380 mL.

Following drug administration, subjects will fast for a period of 4 hours until lunch. During fasting, no fluids are allowed except water; however, water is not allowed from 1 hour predose until 1 hour postdose (apart from the water taken with the dose).

Subjects will not lie down for 4 hours after drug administration, except when required for assessments that need to be performed.

